We propose to enroll 600 AMSM and maintain a sample of 500 AMSM. We will use census information of population structure by race/ethnicity for each region to inform our recruitment goals. We will calculate the number of men in the eligible age group and by race/ethnicity in each region, and use data from the Youth Behavioral Risk Factor Surveillance System (YRBS) to estimate the proportion of AMSM in each age group who could meet eligibility criteria (based on same sex behavior, identity, or attraction), and apply that age-specific proportion to the estimated total AMSM population by race in each region. This will result in an estimated number of eligible AMSM per region and racial/ethnic group. Based on these calculations, to recruit a sample that is diverse in terms of race/ethnicity, we will need to oversample some racial/ethnic subgroups substantially. We will enroll a total of 150 AMSM from each of the 4 regions listed above. As noted, these regions were selected to represent variations in socioeconomic status, HIV prevalence, and rurality. Based on our estimates, we propose to sample such that at least 50% of our sample is a racial or ethnic minority, and at least 35% of participants being from rural areas across the regions. We recognize the challenge of recruiting early adolescents, especially because same sex attraction and same sex sexual experience become more common with age. Therefore, we realistically expect to include a greater number of participants in older age groups. These procedures will provide power for an analysis of efficacy stratified by age and race/ethnicity. Our expected sample size for analyses across both conditions is N=500 (Intervention, n=250; Control, n=250), assuming a 15-20% loss to follow-up. We estimated the minimum detectable effect sizes at 80% power, for comparisons of the two groups for the continuous primary cognitive (e.g., behavioral intentions, attitudes, norms, self-efficacy) outcomes, as well as the difference in the proportion of AMSM who report increased behavioral in the outcomes (e.g., condom use, HIV testing) to engage in HIV prevention services and behaviors in our treatment arm (iReach) vs. our attention-control arm. For mean differences, our sample size calculations are based on a two-sample t-test assuming equal variance using a two-sided significance of 0.05. At 80% power, we are able to detect a between-arm difference of $d=0.22$ at the final follow-up. For repeated measure analyses, assuming a within-person correlation of 0.25, we would be able to detect a difference of 0.08. A less favorable within-person correlation of 0.75 allows us to detect an effect size of 0.11. For proportions, our sample size calculations are based on a two-sample test of proportions using a two-sided significance of 0.05. To have 80% power to compare active treatment to the control group, we require at least 500 participants to find a 12.5% difference between treatment and control in cross-sectional analyses. Assuming within person correlation of 0.25, we can detect an 8.8% difference. A less favorable within-person correlation of 0.75 allows us to detect an 11.3% difference

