Eligible individuals must (1) have been assigned a male sex at birth and identify as male at the time of enrollment into the study (cis-gender male), (2) be between the ages of 13 and 18 years (inclusive), (3) speak and read English, (4) report same-sex attractions and/or behaviors, (5) have access to the Internet, (6) live in one of the zip codes at least partially contained in the 109 counties included in the four regions selected for this trial, and (7) self-report as HIV-negative at time of enrollment.

Randomization and Blinding

Participants are randomized on a 1:1 basis using a stratified randomization by race and region. AMSM will be randomized to one of two arms, with 300 randomized to each arm (complete data on 250 AMSM per arm, allowing for attrition of 50 AMSM per arm).

Study Assessments

The proposed domains mirror the theoretical framework informing our intervention. We include a summary of the primary and secondary outcomes, key intervention mechanisms of change, and potential covariates. Assessments will not take more than 25 minutes to complete. We have taken several steps to ensure that the assessments are brief and developmentally appropriate. First, AMSM will not answer all listed constructs at every assessment. Identity-related constructs, for example, will be measured at 6-month intervals, whereas other constructs (e.g., comfort discussing sexuality) will be assessed at each follow-up. Second, consistent with best practices that we have used in prior HIV studies with pediatric and adolescent populations^{142,256}, we will use gate-keeping questions to decide whether participants should receive other probes within a domain. For example, a participant who has yet to become sexually active would receive cognitive assessments focused on HIV risk and awareness (e.g., attitudes, norms), but would not receive questions regarding behavioral intentions to engage in HIV prevention in next 3 months (e.g., HIV testing, PrEP) or questions regarding sexual risk behaviors (e.g., sexual behavior, HIV testing, PrEP use). Similarly, at each assessment, AMSM with no lifetime substance use will not be asked about additional substance use questions. Among sexually active participants, gatekeeping also provides opportunities to regulate how detailed the assessments will be.

Domain	Assessment time					
	Baseline	Month 3	Month 6	Month 9	Month 12	Month 15
Primary outcomes						
HIV knowledge	X		X		X	X
Condom use/communication efficacy	X		X		X	X

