HIV/STI testing	X		X		X	X
Outcomes required for analysis						
Demographics	X		X		X	X
Patient provider communication around sexual orientation		X		X		
Stigma		X		X		
Resilience		X		X		
Psychological needs	X		X		X	X
Future life goals		X		X		
Secondary outcomes						
Internalized homonegativity	X		X		X	X
PrEP use and willingness [X		X		X	X
Sex behaviors	X		X		X	X
Substance abuse	X		X		X	X
Depression	X		X		X	X
Anxiety	X		X		X	X
Self-Esteem	X		X		X	X
Covariates						
Peer influence		X		X		
Family support		X		X		
Discrimination		X		X		
Online behaviors		X		X		
Societal reaction to sexual orientation		X		X		
Ethnicity beliefs		X		X		
Relationship history	X		X		X	X
Intervention acceptability		X				

Sample Size

Our expected sample size for analyses across both conditions is N=600 (Intervention, n=300; Control, n=300), assuming a 15-20% loss to follow-up. We estimated the minimum detectable effect sizes at 80% power, for comparisons of the two groups for the continuous primary cognitive (e.g., behavioral intentions, attitudes, norms, self-efficacy) outcomes, as well as the difference in the proportion of AMSM who report increased behavioral in the outcomes (e.g., condom use, HIV testing) to engage in HIV prevention services and behaviors in our treatment arm vs. our attention-control arm. For mean differences, our sample size calculations are based on a two-sample t-test assuming equal variance using a two-sided significance of 0.05. At 80% power, we can detect a between-arm difference of $d=0.22$ at the final follow-up. For repeated measure analyses, assuming a within-person correlation of 0.25, we would be able to detect a difference of 0.08. A less favorable within-person correlation of 0.75 allows us to detect an effect size of 0.11. For proportions, our sample size calculations are based on a two-sample test of proportions using a two-sided significance of 0.05. To have 80% power to compare active treatment to the control group, we require at least 500 participants to find a 12.5% difference between treatment and control in cross-sectional analyses. Assuming within-person correlation of 0.25, we can detect an 8.8% difference. A less favorable within-person correlation of 0.75 allows us to detect an 11.3% difference.

Timing of Analyses

Final analysis will be conducted once the desired sample size is recruited has reached and completed the last study assessment.

Analysis Populations

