Analysis tests the efficacy of the iREACH intervention as compared to a delayed intervention condition, to create positive changes in the following outcomes: *primary outcomes*: changes in confidence to engage in HIV prevention behaviors and changes in HIV knowledge and *secondary outcomes*: changes in sexual behavior and change in HIV testing behavior over the 12-month follow-up period. Descriptive statistics of the behavioral, psychosocial, and demographic characteristics of the participants will be described for all and by group (intervention and control). These will be compared between treatment groups using t-tests or Wilcoxon rank sum tests for continuous variables and chi-square tests for categorical variables. In addition, we will use the general framework of generalized linear mixed models (GLMM) to test for intervention effects over time. Note that some of our outcomes are binary, some count and some continuous traits and thus need to be treated differently. The general form of the GLMM will be $(\mu_{ij}) = \beta_{0i} + \beta_{\text{cov Covariates}_{ij}} + \beta_{\text{Time}_{j}} + \beta_{\text{Intervention Group}_i} + \beta_{\text{Group} \times \text{Time}_i}$, where μ_{ij} is the mean response corresponding to subject i at Time j (baseline and 4 follow-ups) with the appropriate link function (identity for continuous outcome, logit for binary outcome and natural log for count outcomes); Group =1 if the i -th subject is in the intervention group and 0 if the i -th subject is in the attention-control group. The interaction coefficients $\beta_{\text{Group} \times \text{Time}}$ are of interest here, measuring the difference in the rate of change in outcomes across the two treatment groups over time in the primary and secondary outcomes. Models will be compared according to information criterion like AIC, BIC. For some binary outcomes like HIV testing, we will perform an aggregate analysis after collapsing across the repeated measures using simple logistic regression comparing whether the probability of having tested at least once over the entire FU period is different across treatment groups, after adjusting for baseline values. To ensure robustness, we will also apply an exchangeable working correlation structure to its corresponding generalized estimating equation (GEE) model.

Reporting Conventions

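### The repeated-measures detectable effects 0.08 and 0.11 have no stated metric and are not for the planned Group × Time test, for which a correlation of 0.75 is the more favourable case

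*SAP*

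**What the plan says.** The Sample Size section of the SAP and the Target Population and Accrual section of the Protocol share one power paragraph. It gives a two-sample t-test result of d=0.22 at the final follow-up (two-sided 0.05, 80% power). It continues "For repeated measure analyses, assuming a within-person correlation of 0.25, we would be able to detect a difference of 0.08" and then "A less favorable within-person correlation of 0.75 allows us to detect an effect size of 0.11". For proportions it gives a 12.5% cross-sectional difference, then "Assuming within-person correlation of 0.25, we can detect an 8.8% difference", and 11.3% at a correlation of 0.75.

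The sample size behind these figures differs between places. The SAP's Sample Size section says "Our expected sample size for analyses across both conditions is N=600". The Protocol says "Our expected sample size for analyses across both conditions is N=500 (Intervention, n=250; Control, n=250". The SAP's Randomization and Blinding section agrees with the Protocol: "complete data on 250 AMSM per arm, allowing for attrition of 50 AMSM per arm".

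The efficacy analysis is a generalized linear mixed model with a subject-specific intercept. The SAP (Efficacy Analyses) names the Group × Time coefficients as the quantity of interest, "measuring the difference in the rate of change in outcomes across the two treatment groups over time in the primary and secondary outcomes". The Protocol (Statistical Analysis) says the same, describes normally distributed random intercepts, and leaves a random slope to be explored.

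Both documents describe the model as using baseline plus four follow-ups. The SAP's schedule table, however, places HIV knowledge and "Condom use/communication efficacy" at baseline and months 6, 12 and 15. Month 15 is surveyed in the control arm only (Protocol, Subject Follow-up), so the two-arm comparison has three time points for these outcomes.

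**The concern.** A reader who meets 0.08 and 0.11 straight after d=0.22 will take them as d. The trial would then seem able to detect very small effects once the repeated measures are used, and high within-person correlation would seem to be the threat to power.

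Neither impression fits the planned test. A Group × Time term is a within-person contrast, and high correlation between a person's visits makes such a contrast more precise. The plan therefore gives no detectable effect for the coefficient it will test, and it misdirects readers about which correlation is the pessimistic one. Anyone who later judges a null result against 0.08 would be judging it against a figure on another scale and for another test.

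**Working it through.** **Inputs.** Two-sided 0.05, 80% power, 1:1 allocation and correlations ρ = 0.25 and 0.75 come from the Sample Size section. The number per arm is n = 250 (Protocol; SAP Randomization and Blinding) or 300 (SAP Sample Size). Constant correlation follows from the random-intercept model. Complete data are assumed. z = 1.960 + 0.842 = 2.8016.

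**Step 1: reproduce the printed pair.** For an arm difference averaged over k measures,

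d = z·√[(2/n)·(1+(k−1)ρ)/k], and Cohen's f = d/2 for two equal groups.

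Example: n = 250, k = 4, ρ = 0.25 gives d = 2.8016·√(0.008 × 1.75/4) = 0.166, so f = 0.083.

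| k | f at n=250 (ρ 0.25 / 0.75) | f at n=300 (ρ 0.25 / 0.75) |
|---|---|---|
| 2 | 0.099 / 0.117 | 0.090 / 0.107 |
| 3 | 0.089 / 0.114 | 0.081 / 0.104 |
| 4 | 0.083 / 0.113 | 0.076 / 0.103 |
| 5 | 0.079 / 0.112 | 0.072 / 0.102 |
| 6 | 0.077 / 0.112 | 0.070 / 0.102 |

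The pair 0.08/0.11 appears at n = 250 with four, five or six measures. It does not appear at n = 300 for any count from two to six. Doubling the printed values gives d of about 0.16 and 0.22. That the metric is f is an inference; the Protocol labels a different detectable effect (0.18, in Statistical Analysis) as f, which supports it.

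**Step 2: could the pair be d?** As k grows without limit, the averaged d falls to z·√[(2/n)ρ]. With n = 250 this is 2.8016·√(0.008 × 0.25) = 0.125 and 2.8016·√(0.008 × 0.75) = 0.217. Both exceed the printed figures. Baseline adjustment with two averaged follow-ups gives 0.188/0.140, which is not the pair either.

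**Step 3: the test the plan names.** With linear time and a random intercept, the detectable 12-month difference in SD units is

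d₁₂ = 12·z·√[(2/n)(1−ρ)/SSt],

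where SSt = 72 for months 0, 6, 12 and 90 for months 0, 3, 6, 9, 12. Example: 12 × 2.8016·√(0.008 × 0.75/72) = 0.307.

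| Visits | n=250 (ρ 0.25 / 0.75) | n=300 (ρ 0.25 / 0.75) |
|---|---|---|
| 0, 6, 12 | 0.307 / 0.177 | 0.280 / 0.162 |
| five visits | 0.274 / 0.158 | 0.251 / 0.145 |

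Correlation enters only through (1−ρ), so moving from 0.25 to 0.75 multiplies the detectable effect by √(0.25/0.75) = 0.58.

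**Step 4: sensitivity at 0/6/12, n = 250.** A joint 2-df test needs 0.340/0.196 for a linear effect and 0.294/0.170 for a constant one. A random slope with SD 0.2 to 0.5 in 12-month change (assumed) adds (SD/12)² to (1−ρ)/SSt and gives 0.311 to 0.331 / 0.184 to 0.217. The values move, but 0.75 stays the favourable case.

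**Step 5: the proportions pair.** With effective n = 250k/(1+(k−1)ρ) per arm and a control rate of 50% (assumed; unpooled variance), three measures give 8.8%/11.3%, four give 8.2%/11.2% and five give 7.9%/11.1%. With three measures, control rates of 20% and 30% would give about 7.5%/9.9% and 8.4%/10.9%. On the 50% assumption the proportions fit three measures while the means need four to six, so one paragraph appears to use two visit counts.

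**The case against.** **The figures are right for what they are.** For a visit-averaged comparison at 250 per arm the pair reproduces, and 0.75 is then the less favourable correlation. That stands: this is not a slip in arithmetic. But the plan names no visit-averaged test for the continuous outcomes. Its aggregate analysis is a logistic regression for some binary outcomes.

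**Nothing depends on these figures.** The text ties the need for at least 500 participants to the 12.5% cross-sectional difference. That also stands, and it limits the consequence to the power statement.

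**Time coding is not specified, so no single replacement is correct.** This is fair. The values in step 3 are examples under stated assumptions.

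Three stronger readings are tempting but not supported:

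- A reader might divide 0.274 or 0.307 by 0.16 and infer that at ρ = 0.25 the planned test is far weaker than stated. That compares an effect growing linearly from zero with one held constant at every averaged visit. For the same linear effect, the average of four follow-ups needs a 12-month difference of 0.166/0.625 = 0.265 (mean of 0.25, 0.5, 0.75 and 1 is 0.625), against 0.274 for the five-visit slope. Most of the apparent loss comes from effect shape.
- A reader might infer that at ρ = 0.25 Group × Time is worse than a 12-month t-test, which needs 2.8016·√0.008 = 0.251. That depends on coding. For a constant effect, the mean of four follow-ups minus baseline needs 2.8016·√(0.008 × 0.75 × 1.25) = 0.243.
- A reader might infer that attitudes, norms and intentions are not scheduled at all. The table lists domains rather than subscales, and its row for HIV/STI testing may carry some of them.

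**Conclusion.** The point holds as a fault in the power statement and should be fixed. The printed 0.08 and 0.11 have no metric, visit count or test, and they are not d for an unadjusted visit average. The reading that reproduces them is Cohen's f for a time-averaged arm difference with 250 per arm and four to six measures (d about 0.16/0.22). For the planned Group × Time coefficient the ranking of the two correlations is reversed: under a random intercept, 0.75 needs an effect 0.58 times as large as 0.25 does.

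The identification of f is inferred, and the reading of the proportions pair rests on an assumed control rate. The reversal rests on the random-intercept model the plan describes; it also held for the random slopes tried. The documents do not support a conclusion that the trial is too small or that the test is invalid. Whether the printed d=0.22 is itself right is a separate question, and nothing here uses it.

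**What to change.** In the Sample Size text of both documents:

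- Replace or supplement 0.08/0.11 with detectable differences labelled as d for the Group × Time coefficient. State the coding of time, the visits, the correlation structure and one analysable N (250 per arm, reconciled with the SAP's 600).
- If linear time, a single-df test, a random intercept and complete data are assumed at 250 per arm, the entries are 0.307/0.177 for outcomes at 0, 6 and 12 months and 0.274/0.158 for outcomes at all five visits. Note that categorical time, a joint test, a constant effect or a random slope changes them.
- Reverse or delete the description of 0.75 as less favourable for that coefficient.
- If the time-averaged figures are kept, say that they are time-averaged and give them as d (about 0.16/0.22) with the number of measures. Label 8.8%/11.3% in the same way, with its control rate.
- Reconcile the model's baseline plus four follow-ups with the schedule's baseline, 6 and 12 months for the primary outcomes.

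The cost is wording in two documents. No new data are needed, and neither the planned test nor the target enrolment changes.
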